## **METHODS FOR 5 YEAR OLD SURVEY**

---

### **RATIONALE**

---

This survey follows the protocol used in the original CSAG survey which attempted to locate and study all children born with non-syndromic UCLP in defined periods. In addition, the survey will also examine if children with cleft have the same growth development as children without a cleft and examine the psychosocial predictors of outcome such as social and family circumstances, parenting and parental characteristics and child characteristics.

To ensure that we are comparing a similar group of children in the UK, the current study is an observational cross-sectional study of 5-year-olds with UCLP. It is not necessary to survey all children in the UK born with some form of clefting as several multi-centre comparisons have provided evidence that care for and outcomes in, UCLP cases are representative of cleft care across the UK. All of the 5-year-olds born with UCLP in the current study will have been treated within a centralised or centralising service. By the age of 5, children in the UK will have started their formal education and will be speaking to people they are unfamiliar with. Centralized multidisciplinary cleft care teams throughout the U.K. have developed at different rates and have differing models of centralized care. This will allow us to compare differences in the timing of centralisation and a number of different models of care.

### **STUDY SAMPLE**

---

We aim to study all 5-year-old children from cleft centres in the UK born in the two year period between **01/04/2005 to 31/03/2007**. At the time of the audit the child should be aged between 5 years 3 months and 5 years 9 months. The original CSAG survey identified 326 five-year-olds born with UCLP in the UK over a two year period and outcome records were collected

for 239 five-year-olds (1). This represents a recruitment rate of 73%. As care is now centralised and better documented we anticipate that we will be able to obtain information from at least 250 patients born with with UCLP.

## SETTING

---

The majority of children will be seen in research audit clinics run by the cleft centres. Families who would usually attend outreach clinics will be encouraged to come to the central research audit clinic (travel expenses will be offered to cover the cost of attendance). Where this is not possible the children will be assessed in outreach clinics.

## IDENTIFICATION OF ELIGIBLE PARTICIPANTS

---

The cleft centres in the UK will be asked to identify eligible participants by using the inclusion and exclusion criteria. As a cross check, eligible participants will also be identified through the CRANE database. The data manager from the CRANE database will send each cleft centre a list of eligible participants based upon the inclusion criteria, the cleft centre will use this list to validate their own records.

## INCLUSION CRITERIA

---

5 year old children with complete unilateral clefts of the lip and palate, including any with soft tissue bands of less than 5mm, born during the two year period **01/04/2005 to 31/03/2007**. The children will be seen between ages 5.3 to 5.9 years. If a child fails to attend the initial scheduled research audit clinic, they will be invited to attend the subsequent research audit clinic up until the age of 6.5 years. The cleft centres will provide a list of eligible participants with the following indicators: a) year of birth b) sex

## EXCLUSION CRITERIA

---

Children whose developmental delay or syndrome is sufficient to prevent them from co-operating with procedures for data collection, such as;

- No speech
- No (or very little) comprehension
- Other criteria checked on a case by case basis agreed with research team

It is thought important that we do not exclude cases that might have been included in the original CSAG survey. Therefore, we should aim to be as inclusive as possible with full documentation on each case; thus any case that is questionable should be discussed between the cleft centre and the research team and if deemed unsuitable for inclusion, the case will be omitted from the data analyses. Cleft centres will be asked to make available clinical photographs of children who are excluded on the grounds of having soft tissue bands of more than 5 mm.

The cleft centres will also provide a list of the excluded children for the research team for verification that will contain the following details:

Year of birth	Sex	Reason for exclusion

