## **BACKGROUND**

---

Cleft lip and palate (CLP) is one of the most common congenital abnormalities in the UK with an estimated prevalence of 1 in 700 live births (1, 2). Prevalence varies by ethnicity, geographic origin and gender with males more likely than females to have a unilateral cleft lip and palate (UCLP)(3). In addition a left-sided cleft is more common than a right sided cleft (4). Care of a person with cleft lip and palate is complex. It usually begins with antenatal diagnosis and continues into adulthood. Treatment of cleft lip and palate is resource intensive requiring evaluation and care from a range of specialists including Audiologists, Cleft Nurse Specialists, Clinical Geneticists, Clinical Psychologists, Dieticians, Orthodontists, Medical Photographers, Paediatricians, Paediatric Dentists, Restorative Dentists, Speech and Language Therapists, and Surgeons (from ENT, Plastic Surgery, and Maxillofacial Surgery) to achieve the optimum outcome.

In the 1990s concerns were expressed over the standard of care and outcome in children with cleft lip and palate in the United Kingdom (UK) and the training of those health care professionals providing it (5-8). These concerns led the Clinical Standards Advisory Group (CSAG), to commission a national survey of the care and outcome in children with CLP – referred to in this document as the CSAG survey (9, 10). This survey began in 1996 and ran over a 15 month period. The survey aimed to include all non-syndromic children in the U.K., born with a complete UCLP aged either 5 or 12-years of age. The outcomes assessed included the quality of speech, hearing, naso-labial appearance, dental arch relationships, oral health, the success of alveolar bone grafts (in the 12 year old cohort only) and child/parent satisfaction (11-14).

In 1998 the group published their main report (1). Fifty seven centres were identified as providing a cleft service in the U.K. with the number of cases being treated per year varying considerably. They found that the outcomes of cleft care in the U.K. were generally poor. One of the key findings was the poor outcome with respect to dental arch relationships and profile, when compared with three European centres (Oslo, Bergen, and Nantes). It was reported that 36% of 5 year olds and 39% of 12 year olds with UCLP had a poor dental arch relationship. Other centres in Europe have shown outcomes with less than 10% of UCLP cases having poor dental arch relations (1).

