## **POWER CALCULATIONS**

---

In the baseline survey of outcomes in five year old children with CLP nearly 40% had poor dental arch relations; 40% had untreated dental caries and 19% were judged to be impossible to understand or were just intelligible to strangers. With a sample size of 250 children and setting the (2-sided) value of alpha at 0.05 we will have over 90% power to detect an absolute difference in dental arch relations and caries of 20% and over 80% power to detect an absolute difference in intelligible speech of 10%.

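### The current survey and the CSAG benchmark are defined differently on a trait tied to intelligibility, and the current exclusion removes the whole child instead of the speech outcome alone

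*Protocol*

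**What the plan says.** The Protocol's Background gives the benchmark population: "The survey aimed to include all non-syndromic children in the U.K., born with a complete UCLP aged either 5 or 12-years of age". The Rationale of the 5-year-old survey repeats that CSAG "attempted to locate and study all children born with non-syndromic UCLP in defined periods" and says that the current survey follows the same protocol. In both places the only limit besides cleft type and age or birth period is the absence of a syndrome.

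The current Inclusion criteria ask for complete UCLP (allowing soft tissue bands under 5 mm) and birth within a two-year window. They do not mention syndromes. The Exclusion criteria then remove "Children whose developmental delay or syndrome is sufficient to prevent them from co-operating with procedures for data collection, such as" children with no speech, which is the first listed example, or with "No (or very little) comprehension", which is the second. The section goes on: "It is thought important that we do not exclude cases that might have been included in the original CSAG survey". Doubtful cases are discussed between centre and research team, and "if deemed unsuitable for inclusion, the case will be omitted from the data analyses". Centres keep a record of exclusions: "The cleft centres will also provide a list of the excluded children for the research team for verification", with year of birth, sex and reason.

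Intelligibility is one of three outcomes in the Power calculations. The baseline figure is that "19% were judged to be impossible to understand or were just intelligible to strangers".

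**The concern.** Objective 2 is a comparison with CSAG, so the two cohorts need the same definition. As written they differ in two ways.

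- A non-syndromic child with developmental delay and no speech fits the CSAG population as the protocol describes it, but is a named exclusion now.
- A child with a syndrome who can co-operate is eligible now, but lay outside CSAG's stated aim.

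Both differences concern children whose speech may well differ from that of the rest. Eligibility is therefore tied to a powered outcome. The regression adjustment in the Statistical analysis section cannot bring back children who are not in the data.

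The exclusion also applies to the child and not to the speech station. Therapy and ENT history, surgical details from the records, and the parents' psychology, satisfaction and personal-cost questionnaires need no speech from the child. These data are lost too, for the objectives on care provided and family costs, and they concern children who may have high needs.

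**Working it through.** **The plan's own figure.** Inputs are 19% adverse speech, a 10-point difference, two-sided alpha 0.05 and 250 current children (Power calculations), and 239 CSAG children with outcome records (Study sample). For 19% v 9%, the pooled rate is (239 × 0.19 + 250 × 0.09)/489 = 0.139. Power is Φ{[0.10 − 1.96·√(0.139 × 0.861 × (1/239 + 1/250))] / √(0.19 × 0.81/239 + 0.09 × 0.91/250)} = 89.3%. This agrees with the stated figure of over 80% for an improvement. No stated number is in dispute.

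**First mismatch: non-speaking, non-syndromic children dropped now.** Let e be the share of the current eligible cohort removed, all of whom would have been adverse. The protocol gives no value for e, so a range is shown. Assume that CSAG kept and rated such children as adverse, that the true rate is 19% in both eras, and that nothing offsets the loss. The current rate becomes (0.19 − e)/(1 − e). For example, at e = 3% it is 0.16/0.97 = 16.5%. The chance of a significant improvement comes from exact binomial enumeration of the pooled two-proportion z-test, 239 v 250:

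| e | Children per 250 | Current rate | Spurious improvement | Chance of false significant improvement |
|---|---|---|---|---|
| 0 | 0 | 19.0% | 0 | 2.5% |
| 0.4% | 1 | 18.7% | 0.3 points | 3.1% |
| 1.5% | about 4 | 17.8% | 1.2 points | 5.4% |
| 3% | about 8 | 16.5% | 2.5 points | 10.9% |
| 4% | 10 | 15.6% | 3.4 points | 16.6% |

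**Second mismatch: co-operative syndromic children admitted now.** Suppose k adverse children are dropped from 250 and m syndromic children with adverse rate q are added. The current rate is (0.19 × 250 − k + q·m)/(250 − k + m). The values of k, m and q are all assumed.

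- k = 5, m = 10, q = 60%: (47.5 − 5 + 6)/255 = 48.5/255 = 19.0%, so the two effects cancel.
- k = 5, m = 20, q = 40%: (47.5 − 5 + 8)/265 = 50.5/265 = 19.1%, again close to zero.
- k = 0, m = 20, q = 50%: (47.5 + 10)/270 = 57.5/270 = 21.3%, so the current cohort looks 2.3 points worse.

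The net bias can therefore take either sign with modest inputs, and the documents do not supply them.

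**The case against.** The strongest reply is that the protocol does not give CSAG's working exclusions. The Background sentence says what that survey aimed at. It obtained outcome records for 239 of 326 identified children, and non-speaking children may be among the other 87. Judging intelligibility normally needs a speech sample, so both rates may in fact be among children with assessable speech. This stands. A reader might infer that the worst speech outcomes leave only the current cohort and that a false improvement is therefore favoured. The documents do not support that inference, for this reason and because syndromic children who can co-operate are now admitted.

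It is also true that the exclusion concerns delay or syndrome that prevents data collection, not poor cleft speech. Children who speak unintelligibly, or are just intelligible to strangers, stay eligible. Counting every non-speaking child as adverse in the main analysis could itself create an imbalance if CSAG did not do so.

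Nor does every other station survive. The photographs include smiling and whistling views, height measurement asks the child to follow instructions, and the clinic procedure asks for the child's verbal consent. Only record review and parent questionnaires clearly need nothing from the child.

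The safeguards are real but partial. Joint discussion is for questionable cases, whereas absence of speech is a named example. The exclusion list counts the losses and gives reasons, but recovers no outcomes. None of this shows that the two populations match.

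**Conclusion.** The point holds as a mismatch of definition. The current cohort is limited by ability to co-operate and the benchmark by absence of a syndrome. The current rule conflicts with the section's own aim of keeping cases that CSAG might have included. The loss of record-based and parent-reported data follows from the whole-child exclusion and needs no assumption about CSAG.

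The direction and size of any bias in the speech comparison are not established. If only the current cohort loses non-speaking children, the chance of a false improvement rises from 2.5% to about 3%, 5% or 11% at 0.4%, 1.5% or 3% removed. At 3% the shift is 2.5 points against a design difference of 10. These figures depend on the assumed share, on CSAG having rated such children as adverse, and on no offset from syndromic children. The finding is a cheap improvement to comparability, not evidence that the comparison is invalid.

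**What to change.** 1. Apply the exclusion by outcome. A child who cannot give a speech sample is missing for speech only and, with parental consent, still contributes record-based data, the parent questionnaires and any station that the child can complete.
2. Make the main comparison with CSAG among non-syndromic children, using CSAG's actual exclusions where its records show them. This deals with both mismatches.
3. Add a sensitivity analysis that counts excluded non-syndromic, non-speaking children as adverse for intelligibility. Present it as a bound, not as the main analysis.
4. Report the number excluded by reason, from the list that the centres already supply.

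The cost is an eligibility wording amendment, including how the child's verbal consent is handled, a few children with incomplete data, and one or two extra analyses.

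### Eligibility admits children with a syndrome who can co-operate, whereas the CSAG comparator is described as non-syndromic, so comparability on syndrome status is not assured

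*Protocol*

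**What the plan says.** Two places in the protocol describe the comparator. Background: "The survey aimed to include all non-syndromic children in the U.K., born with a complete UCLP aged either 5 or 12-years of age". Rationale of the 5 year old survey: "This survey follows the protocol used in the original CSAG survey which attempted to locate and study all children born with non-syndromic UCLP". The Rationale then gives its purpose: "To ensure that we are comparing a similar group of children in the UK". Objective 2 is the comparison of current outcomes with CSAG outcomes.

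The current Inclusion criteria read "5 year old children with complete unilateral clefts of the lip and palate, including any with soft tissue bands of less than 5mm", followed by the birth window and the age at assessment. They do not mention syndromes. The Exclusion criteria remove "Children whose developmental delay or syndrome is sufficient to prevent them from co-operating with procedures for data collection", with absent speech and absent or very limited comprehension as examples, and add "Other criteria checked on a case by case basis agreed with research team". The same section explains the breadth as a wish not to lose children whom CSAG might have taken. It asks for full documentation, has the cleft centre and the research team discuss questionable cases, and omits from analysis those found unsuitable.

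Statistical analysis plans regression against the earlier outcomes with control for confounding factors, none of them named.

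**The concern.** A child with a diagnosed syndrome who can sit through the assessments is eligible now but lay outside CSAG's stated target. The criteria therefore allow a case-mix difference between the two surveys that has nothing to do with how care is organised, and Objective 2 depends on that contrast. The stated reason for breadth guards against dropping CSAG-type children. It does not guard against adding children whom CSAG did not aim to include.

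If syndromic children have worse results on an outcome, a real improvement would look smaller than it is. This is most plausible for speech, which also has the least spare power of the three outcomes in Power calculations.

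**Working it through.** **Inputs from the protocol.** CSAG outcome records: 239 children (Study sample). Current sample: 250, two-sided alpha 0.05 (Power calculations). Baseline rates: about 40% for poor dental arch relations, 40% for untreated caries, 19% for poor intelligibility. Differences sought: 20, 20 and 10 points.

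**Inputs assumed.** The protocol gives neither the share of included children with a syndrome (*s*) nor their excess risk of a poor outcome over the other children (*d*). I take *s* = 2%, 5%, 10% and *d* = 10, 20, 31, 40, 51 points. With a 9% rate in non-syndromic children, 31 and 51 points correspond to poor-speech rates of 40% and 60%.

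**Formula.** Power = Φ[(|p1 − p2| − 1.96·SE0)/SE1]. SE0 uses the pooled proportion and SE1 the separate proportions.

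**The plan's own figures.** Speech, 19% vs 9%, 239 vs 250: pooled proportion (239×0.19 + 250×0.09)/489 = 0.1389, SE0 = 0.0313, SE1 = 0.0312, so (0.10 − 0.0613)/0.0312 = 1.24 and power is 89.3%. Arch and caries, 40% vs 20%: 99.8%. Both stated lower bounds are reproduced.

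**Effect of mixing.** The observed current rate is the non-syndromic rate plus *s*×*d*. Power for speech:

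| Excess *d* | *s* = 2% | *s* = 5% | *s* = 10% |
|---|---|---|---|
| 10 points | 87.8% | 85.5% | 80.9% |
| 20 points | 86.3% | 80.9% | 70.0% |
| 31 points | 84.5% | 75.2% | 55.9% |
| 40 points | 82.8% | 70.0% | 44.1% |
| 51 points | 80.8% | 63.1% | 30.8% |

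The shift runs from 0.02×10 = 0.2 points to 0.10×51 = 5.1 points. A shift of about 1.1 points takes speech power just below 80%. With no excess risk the shift is zero.

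For arch and caries, the same grid gives at least 94.2% (at *s* = 10%, *d* = 51), even if an excess risk is assumed for these outcomes. The protocol does not suggest one.

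**A possible opposite effect.** The exclusion also removes children with developmental delay and no speech or little comprehension, whether or not they have a syndrome. The protocol does not say that CSAG removed them. If such children were a fraction *e* of the population, all with poor speech, removing them turns 19% into (0.19 − *e*)/(1 − *e*). For *e* = 1%, 2%, 4% this gives 18.2%, 17.3%, 15.6%, a fall of 0.8, 1.7 or 3.4 points in favour of the current service. These values of *e* are assumptions too.

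**Cost of restricting to non-syndromic children.** If 2%, 5%, 10% or 15% of the 250 are set aside, n = 245, 238, 225 or 212. Speech power is 89.0%, 88.5%, 87.5% or 86.4%. Arch and caries power stays at 99.7% or more.

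**The case against.** The best defence is that the breadth is deliberate. CSAG only aimed at, or attempted, non-syndromic coverage, and the protocol does not say how strictly that label was applied. Avoiding the loss of children whom CSAG might have included is a reasonable way to protect comparability. There are also safeguards: eligible children are cross-checked against the CRANE database, questionable cases are discussed jointly, and a list of excluded children with reasons goes to the research team for verification. The surgical assessment takes phenotype from the clinical record onto a form that is not shown, so a syndrome field cannot be called absent. Confounder control is planned, and an analysis plan not available here may define the comparison set.

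Much of this stands. A reader might infer that the comparison is biased against the current service. The protocol does not establish that: it gives no syndromic share, no outcome rates for these children and no direction, and the working shows a possible opposite effect. Nor should a reader infer that the centre alone decides who is omitted, since the research team takes part. Growth is no example of harm here: it is not among the CSAG outcomes listed in Background, and the Rationale compares it with children without a cleft.

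The mismatch itself remains. No safeguard restricts the comparison to CSAG's stated population. Because the comparator aimed to contain no syndromic children, adjusting for syndrome status would in effect set the current syndromic children aside, and that too requires the status to be recorded.

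**Conclusion.** The point holds as an unresolved inconsistency with a cheap remedy; it does not show that the comparison is invalid. The Rationale promises a similar group under the CSAG protocol, while the Inclusion and Exclusion criteria admit children outside CSAG's stated target. Comparability on syndrome status is not assured, chiefly for speech.

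Under the assumed shares and excess risks, speech power for 19% versus 9% lies between about 88% and 31%. The milder combinations still meet the stated over 80%; the harsher ones do not. The conclusions on arch relations and caries are hardly touched. These sizes rest wholly on assumed inputs, and the net direction is unknown once the exclusion of children without speech or comprehension is considered.

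**What to change.** 1. Reconcile the Rationale, Inclusion criteria and Exclusion criteria, stating whether the CSAG comparison is of non-syndromic children.
2. Keep recruitment inclusive, and use the full cohort to describe current care and outcomes.
3. Make sure syndrome status is recorded for every included child, for example with the phenotype data on the surgical form if that form does not already hold it.
4. Make non-syndromic complete UCLP the set for every CSAG comparison, with all included children as a sensitivity analysis.
5. Have the research team and the centre settle syndrome and questionable status before, and blind to, the outcome ratings. For speech the timing is easy, because samples are rated by independent listeners after all centres' data are in. For outcomes measured in clinic, status can be settled when eligibility is identified beforehand.

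The cost is at most one field on an existing form and a sentence or two on the analysis set. The comparison loses a small part of the sample, assumed at 2-15%, and the stated power is kept for all three outcomes.
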